6.1.2 Dosing and Administration

Oral Food Challenge

After informed consent is obtained (and assent when relevant), eligible subjects will undergo an open roasted peanut graded food challenge to 4000 mg of peanut protein to confirm peanut allergy and to determine the amount of peanut protein required to induce an allergic reaction at baseline. An oral food challenge is the gold standard for diagnosis of food allergy. PB2 peanut powder (PB2 Foods, Tifton, GA) will be used exclusively for this challenge, mixed in a vehicle of the family's choice (such as applesauce, pudding, etc.).

Subjects will be instructed to hold medications with strong antihistamine properties for five days prior to the challenge (diphenhydramine, loratadine, desloratadine, cetirizine, levocetirizine, fexofenadine, azelastine). The challenge will not be performed in the setting of acute illness, including febrile illness, asthma exacerbations, and significant flares of atopic dermatitis.

The oral food challenge protocol is outlined in Table 3. The initial oral food challenge will take place under the supervision of a trained Allergy/Immunology investigator and trained Allergy/Immunology nurse at Cleveland Clinic Children's main campus Allergy Clinic, where similar food challenges are routinely conducted. The physician investigator available will be trained in recognition and treatment of IgE mediated food reactions, will be available for immediate evaluation of any signs or symptoms of reaction.

Table 3: Oral food challenge to peanut for enrollment (Study Visit 1)

Time	Dose	Clinician Intervention *
0	5mg	Obtain weight, temperature, heart rate, blood pressure, respiratory rate, and oxygen saturation level. Peak flow will be done on patients 4+ or deemed developmentally appropriate. Full physical examination of ears, oropharynx and nose, lungs, and skin prior to administration of dose
+15 minutes	10mg	Examination of skin and auscultation of lungs prior to dose
+30 minutes	25mg	Examination of skin and auscultation of lungs prior to dose
+45 minutes	50mg	Examination of skin and auscultation of lungs prior to dose
+60 minutes	100mg	Examination of skin and auscultation of lungs prior to dose
+75 minutes	500mg	Examination of skin and auscultation of lungs prior to dose
+90 minutes	1000mg	Examination of skin and auscultation of lungs prior to dose

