Upon enrollment, demographic data will be collected including age, sex, race, history of asthma/atopic dermatitis/allergic rhinitis. The enrolled subjects will present to the Clinical Research Unit for a one day dose escalation. The intent of the initial escalation is to begin and remain at subthreshold levels and identify a safe starting dose for home administration. Any subjects unable to tolerate at least 1.5 mg peanut protein will be discharged.

Active illness or asthma exacerbation will prompt rescheduling of the initial dose escalation. Patients are encouraged to eat foods brought from home before and during dose escalation.

Prior to the first dose, patients will receive the following interventions:

- Blood obtained by venipuncture for baseline laboratory evaluation
 - Peanut specific IgE concentration
 - Peanut component testing (peanut specific IgE concentration for Ara h 1, 2, 3, 8 and 9)
 - Peanut specific IgG4 concentration.
 - Serum samples will be sent to the Cleveland Clinic Main Campus laboratory with the exception of the peanut IgG4 level which will be sent out to the Mayo Clinic.
- Skin prick test to peanut with extracts routinely used for this purpose in clinical practice
 - Negative control (50% glycerin/50%Cocas)
 - Positive control (Histamine base 6mg/mL)
 - Peanut extract 1:20 (Hollister Stier)
 - Apply one drop of each solution to upper back (infants and young children) or forearm (children over the age of 6 able to avoid scratching the extract), and prick through with sterile bifurcated needle to disrupt the top layer of the epidermis. The location used for the skin prick test will remain consistent for each patient throughout the study.
 - The test will be read by the clinician 15 minutes following application. The wheal (raised center) and flare (flat erythematous patch) will be measured horizontally and vertically with an average of these 2 measurements recorded as the diameter.

Table 5: Initial dose escalation (Study Visit 2)

Time	Dose	Clinician Intervention *
0	0.5 mg peanut protein	Obtain weight, temperature, heart rate, blood pressure, respiratory rate, and oxygen saturation level (i.e. vital signs). Peak flow will be measure on patient 4+ or deemed developmentally appropriate. Full physical examination of ears, oropharynx and nose, lungs, and skin prior to administration of dose
+30 minutes	1 mg	Repeat vital signs. Examination of skin and auscultation of lungs prior to dose

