If a subject does not tolerate a dose increase, then the patient will be administered a dose reduced by 25%, with increase to the originally intended dose at the subsequent visit. If the patient still does not tolerate the dose, then the decision on how to proceed will be determined at the investigator's discretion. This may involve temporarily decreasing the subject's dose, making a smaller increase, or prolonging the duration of a given dose. If any subject is unable to reach the goal maintenance dose, then the investigator may decide to continue the subject on a lower maintenance dose for the duration of the study.

Table 6: Dose Escalation Schedule

Dose of Peanut Protein	Week of Protocol
6 mg	0
12 mg	2
25 mg	4
50 mg	6
75 mg	8
150 mg	10
300 mg	12

Home Dosing

All subjects will be offered the opportunity to continue once daily consumption of the maintenance dose after the end of their study participation. This ongoing maintenance therapy is optional and will not be paid for by the study. The subjects will be instructed to otherwise continue a peanut free diet.

Follow Up

The subject will also undergo a final oral food challenge at the final visit (SV10). This food challenge will be double blind and placebo controlled. A double blind placebo controlled food challenge (DBPCFC) is the gold standard for diagnosis of food allergy and is the standard utilized for most oral immunotherapy trials at exit.

Roasted peanut powder will be utilized for the challenge, with oat flour as placebo. An individual will undergo a standard challenge described below (Table 7) with either the roasted peanut or the placebo, blinded to both subject and investigators. The same individual will then undergo a second challenge with the opposite (either peanut or placebo) either later that day or by returning to clinic the following day. Each challenge will be performed by increasing doses up to a final dose of 1000 mg of peanut protein. The individual doses will be 25, 100, 200, 300, 600, and 1000 mg of peanut protein. The highest tolerated dose will be recorded. If a patient reacted to a dose lower than 25 mg of peanut powder during the initial Oral Food Challenge then they will be started at the dose lower than where the reaction occurred for the DBOFC.

A urine pregnancy test will be repeated on all females of child bearing potential before the DBOFC.

Table 7: Double blind oral food challenge to peanut or control oat (SV 10)

Time	Dose	Clinician Intervention *

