7.1 Discontinuation of Study Intervention

Criteria for discontinuing oral immunotherapy in a subject will include:

- Subject nonadherence to OIT, specifically defined by 12 (approximately 10%) nonconsecutive missed doses.
- A life-threatening adverse reaction to OIT, specifically a grade 4 reaction as defined by the Consortium of Food Allergy Research (CoFAR) criteria. See table in Section 8.3.3.1.
- Symptoms suggestive of Eosinophilic Esophagitis (EoE) – i.e. difficulty swallowing, chest pain, persistent heart burn, upper abdominal pain, and/or no response to gastroesophageal reflux disease (GERD) medication

Symptoms suggestive of Eosinophilic Esophagitis (EoE) will prompt discontinuation of oral immunotherapy and begin once weekly symptom monitoring phone calls with study staff. If symptoms fail to resolve after 1 month off therapy, consultation with Gastroenterology will be considered for further evaluation and management.

Discontinuation from oral immunotherapy does not mean discontinuation from the study, and remaining study procedures should be completed as indicated by the study protocol. If a clinically significant finding is identified (including, but not limited to changes from baseline) after enrollment, the investigator or qualified designee will determine if any change in participant management is needed. Any new clinically relevant finding will be reported as an adverse event (AE).

The data to be collected at the time of study intervention discontinuation will include the following:

- Skin prick test to peanut
- Peanut sIgE, peanut component panel, and peanut IgG4

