9.2 Sample Size Determination

The sample of 10 patients will provide >90% power to determine the expected success rate (80%) is greater than a theoretical placebo rate (20%).

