6.3.2 Assessment of Secondary Efficacy Endpoints

Highest tolerated dose and cumulative dose. The highest dose of roasted peanut protein tolerated by the subject, cumulative total dose of roasted peanut protein tolerated by the subject, and the changes in highest tolerated dose and cumulative tolerated dose from initial OFC to the peanut protein arm of the exit DBPCFC will be analyzed as ordinal variables because of the interval nature of the dosing schedule (Chinchilli et al., 2005). The dose schedule for initial OFC and exit DBPCFC is shown below.

Peanut protein challenge dose schedule at initial (SV 1) and exit (SV 10) oral food challenges.

Oral food challenge	Highest tolerated dose of peanut protein (mg)	Cumulative tolerated dose of peanut protein (mg) at initial OFC	Cumulative tolerated dose of peanut protein (mg) at exit DBPCFC
Initial only	5	5	
Initial only	10	15	
Initial and Exit	25	40	25
Initial only	50	90	
Initial and Exit	100	190	125
Exit only	200		325
Exit only	300		625
Initial only	500	690	
Exit only	600		1225
Initial and Exit	1000	1690	2225
Initial only	4000	5690	

Serum markers of sensitization and tolerance to peanut. Changes in serum markers of sensitization and tolerance to peanut from initial dose escalation visit to final study visit will be analyzed as continuous variables.

Food Allergy Quality of Life Questionnaires (FAQQLQ). The Food Allergy Quality of Life Questionnaire – Parent Form (FAQQLQ-PF) will be used for patients aged 0-12 years (DunnGalvin et al., 2008). The Food Allergy Quality of Life Questionnaire –Teenager Form (FAQQLQ-TF) will be used for patients aged 13-17 year (Flokstra-de Blok et al., 2008). For all FAQQLQ surveys, all questions are scored on an ordered scale from 1 (“no impairment”) to 7 (“maximal impairment”) for calculations. Subscale and summary scores are calculated as item mean scores, on the same scale from 1 to 7. Subscale and summary scores, and changes in subscale and summary scores from enrollment/baseline visit to final study visit, will be analyzed as continuous variables. The MID (minimally important difference) for the FAQQLQ is 0.5 (DunnGalvin et al., 2010), and the change in total score will be dichotomized as greater than or equal to 0.5 or less than 0.5 and analyzed as a binary variable. Scoring of the FAQQLQ is detailed in section 9.3.2.

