8.2.2 Efficacy Population

- *All patients who completed both initial OFC and exit DBPCFC.*

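### The exit challenge names no start dose for a child who reacted at 5 mg, and the SAP scores any tolerated exit dose below 5 mg as a gain

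*Protocol*

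**What the plan says.** Protocol 6.1.2 uses two different ladders of roasted peanut protein. The baseline challenge (Table 3) runs 5, 10, 25, 50, 100, 500, 1000, 4000 mg. The exit challenge (Table 7) runs 25, 100, 200, 300, 600, 1000 mg. There is one exception to the 25 mg exit start. It covers children whose baseline reaction came at a step under 25 mg, and its instruction is that "they will be started at the dose lower than where the reaction occurred for the DBOFC". No start dose in mg is given, and no steps between the lower start and 25 mg are listed. The summary of changes (entry of 10.01.2019) records that smaller doses might be needed for individual patients, depending on the baseline challenge.

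SAP 6.3.2 sets out both ladders under the title "Peanut protein challenge dose schedule at initial (SV 1) and exit (SV 10) oral food challenges". It marks 5 and 10 mg as *Initial only* and has no exit row below 25 mg.

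SAP 9.2.2 gives a score of zero when the first dose offered is not tolerated. Otherwise the score is the largest dose marked as tolerated on the CRF. The change is exit minus baseline. SAP 10.2 tests the change with a two-sided Wilcoxon signed rank test at 0.05, with a sign test as sensitivity analysis. The population is "All patients who completed both initial OFC and exit DBPCFC" (SAP 8.2.2).

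**The concern.** The most sensitive children are measured from a different bottom step at the two challenges. A baseline score of 0 for a child who reacted at 5 mg means only that the tolerated dose lies below 5 mg, because nothing smaller was offered. If the exit challenge offers something smaller, the same child can record a non-zero score with the same sensitivity. Any sensible choice of low start has this effect under the stated scoring rule, and different choices give different scores.

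Such a child can reach the analysis. At the initial escalation, "Any subjects unable to tolerate at least 1.5 mg peanut protein will be discharged"; the others continue, and Protocol 6.1.2 lets a child stay on a lower maintenance dose to the end of the study. Under Protocol 7.1, "Discontinuation from oral immunotherapy does not mean discontinuation from the study, and remaining study procedures should be completed as indicated by the study protocol". What is at stake is that a child without demonstrated benefit enters the dose-change tests on the side of benefit, where a score of zero would be neutral.

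There is also a plain inconsistency. The protocol starts a child who reacted at 10 mg at 5 mg, while SAP 6.3.2 says 5 mg is not used at exit.

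**Working it through.** **Inputs.** Ladders: Protocol 6.1.2, Tables 3 and 7. Scoring: SAP 9.2.2. Tests: SAP 10.2. Assumed, because the documents give none: the low start dose *d*, tried at 0.5, 1, 2 and 4 mg. Also assumed: the CRF has an item for that dose.

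**1. The plan's own figures.**
- The running sums reproduce the SAP 6.3.2 table. Baseline: 5, 15, 40, 90, 190, 690, 1690, 5690. Exit: 25, 125, 325, 625, 1225, 2225.
- The power statement also reproduces. With 10 patients and one-sided 0.05, the exact rule is at least 5 responders. P(X ≥ 5 at 20%) = 0.0328 and P(X ≥ 5 at 80%) = 0.9936, above the stated 90%. Nothing below depends on this.

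**2. Who is covered.** Only two baseline steps lie below 25 mg.
- Reaction at 10 mg: the next lower dose is 5 mg.
- Reaction at 5 mg: no lower dose exists in Table 3, Table 7 or SAP 6.3.2. The doses of 0.5, 1, 2 and 4 mg in Table 5 belong to the boiled-peanut escalation, not to the roasted-peanut challenge.

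**3. Scoring with an unchanged threshold.** Let *t* be the smallest dose that provokes a reaction, with *t* at most 5 mg at both challenges.
- Baseline score: 0.
- Exit, *d* below *t*: *d* is tolerated and the next step is not. Score *d*; change = *d* − 0 = *d*. For *d* = 0.5, 1, 2, 4 the change is +0.5, +1, +2, +4 mg.
- Exit, *d* at or above *t*: score 0; change 0.
- Since *d* is below 5 mg, the apparent gain in highest tolerated dose is always under 5 mg.
- Contrast: an unchanged child who reacted at 10 mg scores 5 − 5 = 0.

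For cumulative dose, a single low step gives the same figure. Several low steps could sum to more (0.5 + 1 + 2 + 4 = 7.5 mg). As worded, however, SAP 9.2.2 computes the cumulative change from the highest tolerated doses.

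**4. Effect on the tests (illustration only; exact, two-sided, no ties, apparent gain at rank 1).**
- All changes positive, both tests: p = 2 × (1/2)^n. Five gains: 0.0625. Five plus one apparent gain: 0.031.
- Sign test, 7 gains and 1 loss: 2 × (1 + 8)/256 = 0.070. With 8 and 1: 2 × (1 + 9)/512 = 0.039.
- Signed rank, 7 gains and 1 loss: p = 2 × (number of sets of ranks summing to at most the loss's rank)/2^n. Loss at rank 4 of 8: 2 × 7/256 = 0.055; it becomes rank 5 of 9: 2 × 10/512 = 0.039. At rank 3 it was already below 0.05 (0.039 to 0.027). At rank 5 it stays above (0.078 to 0.055). Only rank 4 crosses.
- Eight gains and no loss: 0.008 to 0.004, significant either way.

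**5. With exit doses below 5 mg left out of the score.**
- Unchanged child who reacted at 5 mg: 0 − 0 = 0.
- Child who reacted at 5 mg, now tolerates 5 mg and reacts at 10 mg: 5 − 0 = +5, a real gain that is kept.
- Exit cumulative dose after a low start: 5; 5 + 10 = 15; 15 + 25 = 40 in place of 25. Each later value is also 15 mg higher: 140, 340, 640, 1240, 2240.

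**The case against.** **The flexibility looks deliberate.** The summary of changes suggests an individual safety rule, and a clinician will choose a sensible low dose. That stands as an explanation of why no dose is printed. It does not repair the scoring, because a sensible low dose is exactly what produces the apparent gain.

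**It is rare and small.** This also stands. The child must have reacted at 5 mg, remain in the study, complete the exit challenge, tolerate the low start and react again at 5 mg. Tolerance of at least 1.5 mg at the initial escalation makes a tolerated low start plausible but not certain, because that dose was boiled peanut and the exit uses roasted. For children who stop treatment, Protocol 7.1 lists only skin and blood tests at that point, so their exit challenge is not assured.

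**The p-value crossings need particular data patterns.** They do, and at the response rate the trial expects (8 gains, no loss) nothing changes. They show the mechanism, not a likely result.

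**Other ladder mismatches are larger.** An unchanged child who reacted at 25 mg is outside the exception, starts at 25 mg and scores 0 − 10 = −10 mg. This is a separate question, and the change proposed here does not make the two ladders comparable throughout. Nor is it a bias that a child who reacted at 10 mg may have no 10 mg step at exit: that is the ordinary coarseness of a stepped challenge, which SAP 6.3.2 acknowledges by treating the doses as ordinal.

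**The CRF is not in the documents.** If it has no item for a dose below 5 mg, the score is undefined rather than positive, because the zero rule applies only when the first dose given fails. A rule is needed either way.

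**Conclusion.** The point holds as a minor one. For a child who reacted at 5 mg, the protocol requires a lower start that no challenge table supplies. The SAP then scores a tolerated dose below 5 mg as a gain of under 5 mg, with no change in threshold shown. That gain is a full positive in the sign test and takes about the lowest rank in the signed rank test, where a zero would add nothing to either side. The conclusion assumes that the CRF records the low dose and that the child tolerates it.

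Three stronger readings are not supported:
- *The primary result is at risk.* SAP 5.2 does mention the highest-dose comparison under its primary heading. But SAP 6.3.2 and 10.2 analyse it as secondary, SAP 8.5 refers to a single primary endpoint and calls secondary tests hypothesis-generating, and the 300 mg response and its power do not use these scores.
- *The effect is likely among 10 children.* The documents do not give the share who react at 5 mg. The complement of the expected 80% response is failure at 300 mg, which is far from a repeat reaction at 5 mg. No frequency can be derived.
- *The threshold is known to be unchanged.* Baseline 0 says only that it was at most 5 mg. The gain is undemonstrated, and a real improvement below 5 mg cannot be seen.

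The by-patient listing planned as SAP Table 2.2 would let a reader spot such a case.

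**What to change.** 1. **SAP 9.2.2.** Add one sentence: exit doses below 5 mg do not count towards the highest or cumulative tolerated dose, and a child who tolerates no dose of 5 mg or more scores 0. This alone removes the apparent gain.
2. **Protocol 6.1.2, Follow Up.** State that a child who reacted at 10 mg starts both exit challenges (peanut and oat) at 5 mg, and a child who reacted at 5 mg starts both at a named dose below 5 mg, for example 2 mg. The child then takes each of 5, 10 and 25 mg not yet given before Table 7 continues at 100 mg. Any named dose below 5 mg gives the same score once item 1 is in place. Starting a child who reacted at 5 mg at 5 mg would also score 0, but it gives up the lower start that the protocol requires.
3. **SAP 6.3.2.** Relabel the 5 and 10 mg rows as also possible at exit for these children, with exit cumulative values of 5 and 15 mg. Add a footnote that their exit cumulative values from 25 mg up are 15 mg higher than shown.

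**Cost.** A few sentences and table entries. Compared with Table 7 as printed, at 15 minutes per step, each exit challenge is 2 × 15 = 30 minutes longer after a 10 mg reaction (5 and 10 mg added) and 3 × 15 = 45 minutes longer after a 5 mg reaction (2, 5 and 10 mg added). Sample size and the primary analysis do not change.

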6.2 Preparation/Handling/Storage/Accountability

The Investigational Drug Service (IDS) will provide secure storage, temperature monitoring, drug accountability, and dispensing of Investigational Product (IP) to comply with the protocol and applicable state and federal regulations related to clinical research.

IP Management

Upon the receipt of the IP, IDS will electronically document lot numbers, expiration dates, and quantity. The supply of roasted peanut powder and boiled peanut powder will be tracked and stored separately.

IP dispensing

IDS will dispense the IP to eligible subjects upon receipt of a valid prescription. The prescription will be scanned to [contact] or faxed to [contact], Monday through Friday, 0700-1600. After reviewing the prescription, the pharmacist will:

1. Weigh the prescribed dose
2. Transfer the prescribed dose into a plastic jar
3. Dispense the quantity of doses prescribed
4. Update drug accountability log**
5. File the prescription in the subjects' tab in the study binder

** Associate the dose, quantity, lot of IP dispensed with subject number and date

IP disposition

Returned or expired IP will be accounted for and then destroyed per department policy.

6.3 Measures to Minimize Bias

This study utilizes a prospective trial design in order to minimize recall bias. In addition, the double blind placebo controlled exit challenge will help minimize bias.

6.4 Study Intervention Compliance

The subjects will have periodically scheduled trips to return the empty medicine cups for monitoring of adherence. In addition, the subjects or their families will complete a log at home recording administration of doses as well as any adverse effects.

6.5 Concomitant Therapy

Data regarding the subjects' concomitant medications will be recorded at each study visit to the Pediatric Allergy Clinic or the Clinical Research Unit. For this protocol, a prescription medication is defined as a medication that can be prescribed only by a properly authorized/licensed clinician. Medications to be reported include concomitant prescription medications, over-the-counter medications such as oral antihistamines, and supplements.

The concomitant use of antihistamines could directly affect the primary endpoint. The use of antihistamines could mask or prevent some symptoms of an allergic reaction such as urticaria or pruritus. Upon enrollment, the treating physician investigator will evaluate the specific indication for antihistamine use and will make a determination regarding continued use or discontinuation. This will be documented within the electronic medical record.

